4.2.3.2 Biomarker Research

Analysis of pre- and post-treatment biopsies

Radiology-guided biopsies will utilize 20-gauge core biopsy needles. Biopsies obtained via an endoscopic approach will utilize standard endoscopic biopsy forceps in which specimens are typically 3-6 mm in diameter. As such tissue samples will be composed of both tumor cells and associated tumor stroma. Fresh tumor samples will be immediately delivered to the laboratory of [name] for both ex vivo tumor/immune/stromal cell culture and expansion as well as histologic analyses. Patients with fresh malignant ascites collected will also be immediately delivered to the lab for ex vivo tumor/immune/stromal cell culture and expansion alone. [name] lab will utilize quantitative spatial image analysis to examine changes in tumor cell-stromal interactions including CD4, CD8, Treg, and MDSC populations pre- and post-therapy.

PD-L1 expression within the tumor, on cancer cells and stromal cells, will be analyzed by immunohistochemistry (IHC). PD-1 expression on tumor infiltrating T cells and circulating peripheral blood mononuclear cell (PBMC) T cells will be analyzed by a combination of IHC and flow cytometry. Immune cell populations will be further analyzed via high dimensional flow cytometry to measure levels of Tregs and MDSCs, which will allow us to calculate the ratio of effector T cells to Tregs and MDSCs, respectively. Ex vivo isolated T cells will also be analyzed for proliferative capacity (CFSE dilution) and cytokine production (IFN- γ and IL-17) after stimulation with anti-CD3 and/or PMA and Ionomycin. Furthermore, by use of multi-color IHC we will determine influences of pembrolizumab+RT treatment on the magnitude and proximity of CD8 T cells to cancer cells within the tumor. Lastly, we will analyze changes in the diversity of T cell repertoire in both PD-1 positive and PD-1 negative T cell populations following pembrolizumab+RT treatment via deep sequencing of the TCR V β CDR3 region. Such changes in T cell repertoire can be suggestive of potential epitope spreading for anti-tumor antigens and reversal of tumor antigen-specific T cell anergy. Genomic analyses utilizing City of Hope's Integrative Genomics Core will also be performed on the corresponding cancer/stromal/immune cell populations via total RNA-seq for coding and non-coding RNAs (including miRNAs).

Performance of these studies will require several highly developed techniques that have been routinely conducted in [name] lab. A prototype BD microfluidic FACS instrument allows for 12-color analysis of low cell numbers, thereby allowing maximal data acquisition out of small sample sizes. A powerful quantitative, spatial image analysis system will enable

us to analyze immune and cancer cells in tissues via 8-color histology. Lastly, [name] lab has considerable expertise in TCR repertoire analysis via deep sequencing, which can yield information on T cell specificity to unknown antigens.

Serum circulating miRNA sequencing

10 mL of whole blood will be collected from each patient at prespecified time points and serum separated per standard procedures. Total RNA will be extracted using Trizol and sent to the Integrative Genomics Core at City of Hope for miRNA-seq. The Integrative Genomics Core is a shared resource at City of Hope and is equipped with all major state-of-the-art microarray and sequencing platforms for genomic studies, including Illumina's Hiseq 2500 and Life Technology's Ion Proton sequencers, Illumina's Hiscan Beadchip system, Affymetrix's GeneChip system, and Agilent's microarray system. With a highly experienced team of bioinformaticians integrated within the core, efficient genomic data analysis services will be provided to convert high throughput data into biologically interpretable results. They have extensive expertise in utilizing both commercial and open-source software tools for sequencing data analysis including but not limited to R/Bioconductor, IGV, Bowtie, TopHat, Cufflinks, Novoalign, MACS, MEME, Transfac, BWA, GATK, Samtools, Gene Set Enrichment Analysis (GSEA), Ingenuity Pathway Analysis and DAVID.

Sequence reads that match human miRNAs in Sanger mirBase will be calculated and analyzed. Circulating whole genome miRNA signatures will be compared to miRNAs sequenced from total RNA-seq from the corresponding tumor biopsy timepoints to aid in biomarker discovery of serum miRNAs that may predict for immunotherapy response or resistance. miR-23a will be of particular interest given its description as a gastric cancer oncomir and function as a repressor of T cell cytotoxicity in preclinical miRNA screens.^{14,15} miR-34a and miR-200 will be other miRNAs of interest to measure given reporting of their ability to suppress PD-L1 expression in other experimental systems.^{16,17}

5.0 METHODOLOGY

5.1 Entry Criteria

Pre-Enrollment Informed Consent and Screening Procedures

Diagnostic or laboratory studies performed exclusively to determine eligibility for this trial will be done only after obtaining written informed consent. Studies or procedures that were for clinical indications (not exclusively to determine study eligibility) may be used for baseline values and/or to determine pre-eligibility, even if the studies were done before informed consent was obtained. The informed consent process is to be fully documented, and the prospective participant must receive a copy of the signed informed consent document. All screening procedures and their respective windows are detailed in the Study Activity Calendar.

Participant Enrollment

COH DCC Availability and Contact Information

Eligible subjects will be registered on the study centrally by the Data Coordinating Center (DCC) at City of Hope.

DCC staff are available between the hours of 8.00 am and 5.00 pm PST, Monday through Friday (except holidays). DCC contact information is as follows:

- [contact] [name]
- E-mail: [contact]

Eligible subjects must be registered **prior** to start of protocol therapy. Issues that would cause treatment delays should be discussed with the Principal Investigator. If a subject does not receive protocol therapy following registration, the subject's registration on the study may be canceled after discussion with the PI. The Data Coordinating Center should be notified of cancellations as soon as possible.

Registration Process

To register a participant the subsequent procedure is to be followed:

1. The study team should contact the DCC via telephone or email to provide notification regarding the pending registration and communicate desired timeline of the registration, especially if it must be completed promptly to meet the registration window.
2. The protocol nurse or CRC will email a copy of the following documents to the DCC:
 - Completed eligibility checklist (printed from [Section 5.1](#) of the protocol)
 - Signed Informed Consent
 - Signed subject's bill of Rights
 - Signed HIPAA authorization form and
 - Provide copies of source documentation only if not readily available as a finalized record in the COH Electronic Medical Record (EMR).
3. After having received all transferred documentation, the DCC will complete the review the documents to verify eligibility, working with the study team as needed to resolve any missing required source elements. A participant failing to meet all protocol eligibility requirements will not be registered.
4. Once eligibility has been confirmed, DCC staff will register the participant by: assigning a subject accession number, register the subject on study centrally into a COH clinical trials management system (e.g. MIDAS), and enter the subject into the eCRF system, Medidata RAVE.

5. Once registration has been completed, DCC staff will send a Confirmation of Registration Form within 24 hours, including the participant study number to:

- The site study team: Principal Investigator, treating physician, protocol statistician, protocol nurse, CRC and COH IDS Pharmacy.
- the COH sponsor team designees

Screen Failures and Registered Participants Who Do Not begin Study Treatment

The DCC is to be notified of all participants who sign consent but do not meet eligibility criteria or do not initiate protocol therapy.

5.1.1 Inclusion Criteria

Participants must meet all of the following criteria on screening examination to be eligible to participate in the study:

Patient MRN:

Patient Initials: (F,M,L):

Informed Consent and Willingness to Participate

- 1. Documented informed consent of the participant
- 2. Willing to provide tumor tissue amenable to ultrasound or CT-guided biopsy for biomarker analyses.
 - Patients with malignant ascites are permitted to participate and provide ascites samples for biomarker analyses.
 - Patients receiving radiation to a single metastatic site in which only the primary tumor is accessible for biopsy by endoscopy will also be eligible.

Age Criteria, Performance Status and Life Expectancy

- 3. Age: ≥ 18 years
- 4. ECOG performance status of ≤ 1
- 5. Life expectancy of ≥ 3 months

Nature of Illness and Treatment History

- 6. Diagnosis of metastatic squamous cell carcinoma and/or adenocarcinoma of the esophagus, gastroesophageal junction, or stomach in need of palliative radiotherapy to the primary tumor or a single metastatic site for symptoms such as pain, dysphagia, and/or gastrointestinal bleeding.
 - Patients with adenocarcinoma histology and known HER2-overexpressing disease are permitted to participate if they progressed or are intolerant of prior trastuzumab-containing therapy.

- ___ 7. Measurable metastatic sites of disease outside of the target lesion undergoing palliative radiation based on RECIST 1.1 as assessed by the investigator.
- ___ 8. Have no limits on prior lines of therapy or may be treatment-naïve if in need of palliative RT provided the patient has not received prior anti-PD-1, anti-PD-L1, or anti-PD-L2 therapy.

Laboratory Criteria (within 10 days of treatment initiation unless indicated otherwise)


 ___ 9. ANC $\geq 1,500/\text{mm}^3$ ___ 10. Platelets $\geq 100,000/\text{mm}^3$ ___ 11. Hemoglobin $\geq 9 \text{ g/dL}$ 
 ▪ May receive transfusion to meet this goal as it is anticipated a subset of patient will require palliative radiation to a bleeding primary tumor ___ 12. Total serum bilirubin $\leq 1.5 \times \text{ULN}$ 
 OR Direct bilirubin $\leq \text{ULN}$ if total bilirubin levels $> 1.5 \times \text{ULN}$ ___ 13. Albumin $\geq 2.5 \text{ mg/dL}$ ___ 14. AST and ALT $\leq 2.5 \times \text{ULN}$ OR $\leq 5.0 \times \text{ULN}$ if liver metastases present ___ 15. Serum creatinine $\leq 1.5 \times \text{ULN}$ 
 OR Creatinine clearance^a $\geq 60 \text{ mL/min}$ if creatinine levels $> 1.5 \times \text{ULN}$ 
 ▪ GFR can also be used in place of creatinine or CrCl ___ 16. If not receiving anticoagulants: International Normalized Ratio (INR) OR Prothrombin (PT) $\leq 1.5 \times \text{ULN}$ If on anticoagulant therapy: PT must be within therapeutic range of intended use of anticoagulants ___ 17. If not receiving anticoagulants: Activated Partial Thromboplastin Time (aPTT) $\leq 1.5 \times \text{ULN}$ If on anticoagulant therapy: aPTT must be within therapeutic range of intended use of anticoagulants 	ANC: _____ Date: _____ Plts: _____ Date: _____ Hgb: _____ Date: _____ ULN: _____ Date: _____ Bil: _____ Direct Bil: _____ Albumin: _____ Date: _____ ULN: _____ Date: _____ ALT: _____ ULN: _____ Date: _____ AST: _____ ULN: _____ Date: _____ Serum Cr: _____ Cr Cl: _____ ULN: _____ Date: _____ INR: _____ PT: _____ ULN: _____ Date: _____ aPTT: _____
---	---

____ 18. Negative urine or serum pregnancy test (female of childbearing potential only)
 
 ▪ If the urine test is positive or cannot be confirmed as negative, a serum pregnancy test will be required 	Urine test:	Date:
	Serum test:	

Contraception

____ 19. Female of childbearing potential: willing to use 2 methods of birth control or be surgically sterile, or abstain from heterosexual activity for the course of the study through 120 days after the last dose of study medication.

- Childbearing potential defined as not being surgically sterilized or have not been free from menses for > 1 year.

____ 20. Male: Use an adequate method of contraception starting with the first dose of study therapy through 120 days after the last dose of study therapy.

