2.0 TRIAL DESIGN

2.1 Trial Design

This is a single-arm, prospective, phase II, biomarker analysis trial of pembrolizumab in combination with palliative radiotherapy for patients with metastatic squamous cell or adenocarcinoma of the esophagus, stomach, or gastroesophageal junction (GEJ). We will enroll 14 patients within our institution who are in need of palliative radiation for symptoms related to their primary tumor including pain, dysphagia, and bleeding. Patients with a single metastatic site in need of palliative radiation (e.g., pain from a bony metastasis, enlarged lymph nodes, liver metastasis, etc.) will also be eligible provided they have other measurable metastatic sites outside of the radiation field. The exception will be patients who require palliative radiation to a symptomatic central nervous system (CNS) metastasis. The first dose of palliative radiation and first dose of pembrolizumab will commence on cycle 1, day 1.

Participation in this trial will be dependent on patients having a metastatic site amenable to ultrasound and/or CT-guided biopsy, inclusive of patients with malignant ascites amenable to ultrasound-guided aspiration, and agreeing to provide pre- and post-treatment biopsies for the

IRB Protocol No. 16099

Version: 04

[figure not shown]
Version Date: 10/16/2019

biomarker analysis primary endpoint of the study. Patients who are undergoing palliative radiation for a single target metastatic site, and only the primary tumor is amenable to biopsy are also eligible to participate if they consent to endoscopic pre- and post-treatment biopsies.

Treatment will continue until documented clinical PD, unacceptable AE(s), intercurrent illness that prevents further administration of treatment, investigator's decision to withdraw the patient, patient withdraws consent, pregnancy of the subject, noncompliance with trial treatment or procedure requirements, completion of 35 administrations (approximately 2 years) of treatment with study medication or achievement of a complete response.

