We propose a prospective trial to assess pre- and post-treatment biopsies of patients' metastatic sites with the hypothesis that tumor cytotoxic T cells will be increased with combining pembrolizumab and palliative RT with corresponding improvement in clinical activity. As we will only be radiating a single target lesion in this study population, assessment of response among non-irradiated metastatic sites will serve as a true measure of the abscopal effect. Toxicities are not anticipated to be overlapping for these two modalities, though safety should still be assessed in this early cohort of patients to ensure immune-mediated or radiation-induced toxicities are not exacerbated by the combination. At City of Hope where patients will be solely recruited for this trial, we have extensive experience in the conduct of pre- and post-treatment biopsy studies having completed accrual to a pilot trial of the novel nanopharmaceutical CRLX101 in this disease subset (Clinicaltrials.gov, NCT01612546). We also have a broad gastroesophageal cancer patient population evaluating more than 60 new cases per year due to our institution serving the diverse, multicultural population of the San Gabriel Valley in Los Angeles County. [name], MD, Chair of the Department of Immuno-Oncology, will serve as a collaborating investigator on this study given his laboratory's expertise in translational analyses of tumor/immune/stromal cell interactions.

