4.2.3 Rationale for Endpoints

4.2.3.1 Efficacy Endpoints

The clinical efficacy of combining pembrolizumab and palliative radiotherapy will be measured by assessing overall response rate by RECIST 1.1 and irRECIST. To truly measure the abscopal effect, patients will be required to have metastatic disease sites outside the field of palliative radiation that are considered measurable by RECIST 1.1.

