5.2.3 External Beam Radiotherapy

5.2.3.1 General Radiotherapy Information

The intent of treatment is to deliver a palliative course of radiotherapy to a total dose of 30 Gy in 10 fractions to the symptomatic primary disease sites in the esophageal, GE junction, or gastric areas or one of the metastases. Both 3D conformal radiotherapy and IMRT are allowed.

Megavoltage equipment with effective photon energies \geq 6MV is required.

Technique: 3D conformal using opposed AP-PA portals or multifield techniques, such as AP, PA and opposed lateral fields or IMRT are recommended. ICRU-50 and ICRU-62 prescription methods and nomenclature shall be used in this trial. Tightly contoured targets should be used to spare as much bone marrow, small bowel, liver, heart, lung and kidney as possible.

The prescription volume is the planning target volume (PTV). The total dose is 30 Gy in 10 fractions. A minimum of 90% of the PTV will receive 30 Gy. No more than 10% of the PTV shall receive greater than 35 Gy.

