5.2.3.3 Treatment Planning and Target Volumes

Gross Target Volume (GTV): The GTV is defined as the primary tumor in the esophageal/GE junction/gastric areas, the grossly enlarged lymph nodes, or the gross metastatic sites requiring a palliative course of radiotherapy.

Clinical Target Volume (CTV): Since the intent of radiotherapy is for palliation, there is no need to define a CTV for treatment.

Planning Target Volume (PTV): Margins shall be added to the GTV for set up error and movement as PTV. This expansion could be 0.5 to 2 cm and does not need to be uniform in all dimensions. 4DCT scan is allowed to customize PTV expansion.

3D conformal radiotherapy or IMRT should be planned to optimize the PTV coverage and a minimum of 90% of the PTV shall receive 30 Gy. No more than 10% of the PTV shall receive greater than 35 Gy. IMRT can be delivered by tomotherapy or TrueBeam using RapidArc technique.

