7.1.2.6.1 Initial Tumor Imaging

To meet screening criteria, initial tumor imaging must be performed within 21 days prior to start of cycle 1, day 1. This scan will be considered the baseline assessment for the study. The site study team must review pre-trial images to confirm the subject has at least one target lesion (i.e. meets measurability requirements) per RECIST 1.1.

Scans performed as part of routine clinical management are acceptable for use as the baseline scan if they are of diagnostic quality, include all required anatomy, and performed within 21 days prior to start of treatment.

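### Inclusion 7 asks for measurable disease outside the irradiated lesion, while 4.2.3.1 requires it outside the radiation field, so a patient whose only measurable lesion is in the field can be registered and counted in the response rate

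*Combined protocol and SAP*

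**What the plan says.** Three sections of the combined protocol and SAP state the entry requirement for measurable disease, and they differ.

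- **5.1.1, inclusion 7:** "Measurable metastatic sites of disease outside of the target lesion undergoing palliative radiation based on RECIST 1.1 as assessed by the investigator". The radiation field is not mentioned.
- **4.2.3.1, all patients:** "patients will be required to have metastatic disease sites outside the field of palliative radiation that are considered measurable by RECIST 1.1".
- **2.1, only patients irradiated at a single metastatic site:** they are eligible "provided they have other measurable metastatic sites outside of the radiation field".

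The reason for the requirement is given in 4.2.1: "assessment of response among non-irradiated metastatic sites will serve as a true measure of the abscopal effect".

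On radiation geometry, 5.2.3.1 allows "3D conformal using opposed AP-PA portals or multifield techniques", or IMRT. For the margin from GTV to PTV, 5.2.3.3 says: "This expansion could be 0.5 to 2 cm and does not need to be uniform in all dimensions".

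On checking at entry, 5.1 bases registration on a completed eligibility checklist printed from that section. The coordinating center then verifies eligibility. The baseline imaging check in 7.1.2.6.1 asks the site to "confirm the subject has at least one target lesion (i.e. meets measurability requirements) per RECIST 1.1". It does not ask where that lesion lies in relation to the field.

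**The concern.** Item 7 is the wording that the study team completes at registration, and it is looser than the requirement it should carry out. A measurable metastasis can be separate from the irradiated lesion and still sit inside the margin or in the path of the beams. If it is the patient's only measurable lesion, the patient meets item 7 and fails 4.2.3.1.

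Such a patient has no RECIST lesion that was spared radiation. A response there could come from direct radiation, from pembrolizumab, or from both. Section 9.2 defines a safety population but no response-evaluable population, so nothing in the plan takes this patient out of ORR. Section 9.2 also says that no responses among the 14 patients would reduce enthusiasm for the combination. One in-field response would be enough to avoid that signal, without any shrinkage outside the field.

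**Working it through.** **Step 1: can a patient meet item 7 and fail 4.2.3.1?**

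- Item 7 is met by a measurable metastatic lesion other than the irradiated one.
- Section 4.2.3.1 is met only if a measurable metastatic lesion lies outside the field.
- The field is larger than the lesion. The PTV adds 0.5 to 2 cm to the GTV, and opposed or multifield beams also cross tissue beyond the PTV.
- So a separate lesion close to the target, or in a beam path, can meet the first condition and not the second.

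**Step 2: does anything else close the gap?** The exclusion criteria in 5.1.2 do not mention it. The baseline check in 7.1.2.6.1 is satisfied by any one target lesion. The pre-simulation imaging review in 5.2.3.2 serves to set target volume and field borders; it is not an eligibility check. No listed step compares measurable lesions with the field before registration.

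**Step 3: reproduce the plan's response figure.** Inputs from 9.2: n = 14, true response rate 21%, stated chance of at least one responder 96%.

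P(at least one responder) = 1 − (1 − 0.21)^14 = 1 − 0.79^14 = 1 − 0.0369 = 0.963. The stated figure is reproduced.

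**Step 4: effect on the chance of an out-of-field responder.** Let k be the number of patients with no measurable out-of-field lesion. The documents do not give k, so a range of 0 to 4 is assumed. The plan's 21% is applied as the chance of an out-of-field response in each of the other 14 − k patients:

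P = 1 − 0.79^(14 − k)

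| k (assumed) | Patients with an out-of-field lesion | 0.79^(14 − k) | P(at least one out-of-field responder) |
|---|---|---|---|
| 0 | 14 | 0.0369 | 96.3% |
| 1 | 13 | 0.0467 | 95.3% |
| 2 | 12 | 0.0591 | 94.1% |
| 3 | 11 | 0.0748 | 92.5% |
| 4 | 10 | 0.0947 | 90.5% |

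**Step 5: effect on ORR.** Each patient is 1/14 = 7.1% of the response sample, so one in-field response adds 7.1 percentage points to the observed ORR.

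**The case against.** The strongest reply is that the field rule is already in the protocol. Section 4.2.3.1 states it as a requirement for all patients, 5.1 bars registration of anyone who fails any protocol eligibility requirement, and this is a single-site trial whose stated interest is non-irradiated disease. A careful reviewer could apply the rule. That stands as mitigation. It does not make the checklist prompt for the field, and item 7 is the line that gets completed.

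A second reply concerns nodes beside the primary. Section 5.2.3.3 lists grossly enlarged lymph nodes within the GTV, so such a node may be part of the irradiated target and already fail item 7. Section 5.2.3.1 also asks for tightly contoured targets and allows IMRT. These points make the problem less frequent. They do not cover a measurable lesion that was not contoured as target but lies in the margin or a beam path.

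A reader might also infer more than the documents support:

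- **That 2.1 sets the field condition for everyone.** It attaches the condition only to patients irradiated at a single metastatic site. The all-patient requirement rests on 4.2.3.1.
- **That in-field shrinkage is purely a radiation effect.** Every patient also receives pembrolizumab, for which 4.2.1 quotes response rates of 22.2% and 30.4%. In-field shrinkage is confounded. Equally, in a single-arm trial out-of-field shrinkage cannot be separated from the drug's own effect, so the fix makes ORR readable outside the field but does not isolate an abscopal effect.
- **That such patients are uninformative.** The primary endpoint is the change in T cells, Tregs and MDSCs. Blood, ascites, or a biopsy of a non-measurable out-of-field site can still contribute to it.
- **That the volume added by the margin measures the problem.** How much larger the planned volume is than the lesion does not say how often a patient's only measurable lesion falls inside it.

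**Conclusion.** The mismatch is real and sits in the operative eligibility text. It affects who may enter and whether ORR, which 9.2 calls exploratory, can be read as response outside the field. It does not invalidate the primary biomarker comparison.

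The numerical cost is modest: 1.0 percentage point (96.3 − 95.3) if one patient is affected and 5.8 points (96.3 − 90.5) if four are. These figures rest on an assumed count of affected patients, on the plan's 21% applied to out-of-field response, and on independence between patients. The larger harm is to interpretation, because a confounded in-field response enters ORR unmarked and can on its own avert the zero-responder signal. The sponsor should correct this, since the remedy only carries out a rule that 4.2.3.1 already states.

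**What to change.** Reword inclusion 7 to match 4.2.3.1, for example: *at least one RECIST 1.1 measurable metastatic lesion outside the planned radiation field, as assessed by the investigator*. Define the field in the same place, for example by PTV or by beam aperture; otherwise the ambiguity moves to a new word.

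In 7.1.2.6.1, have the site confirm on the baseline scan, against the intended field, that such a lesion exists, and record each baseline target lesion as in-field or out-of-field. Verify that record on the planning CT when it becomes available. Section 5.2.3.2 requires a planning CT but does not place it before registration, so the check should not force an earlier simulation.

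The cost is one reworded criterion, one confirmation on an existing scan, and one data item per target lesion. N stays at 14. A few candidates may become ineligible; the documents do not allow a count, but 4.2.3.1 already meant to exclude them.
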